## **8 Statistical Considerations**

### **8.1 Clinical Trial Design**

This is a single-center, open label, non-blinded randomized controlled, parallel study designed to evaluate the safety and clinical benefits of banked, allogeneic bone marrow MSCs versus control (routine supportive care) for treatment of COVID-19 related ARDS. The primary safety endpoint will be treatment-related serious adverse events (tSAE), defined in Section 7.4.5. The primary efficacy endpoint will be improvement in clinical status by at least two categories at day 14 post randomization, assessed by a six-category ordinal scale. The study will first enroll and treat 6 patients with MSCs for safety run in, then additional 60 patients will be randomized to receive either MSCs or supportive care designated by their treating physician.

### **8.2 Sample size**

This early phase study will accrue a total of 66 patients with 6 patients for safety run in and additional 30 patients in each treatment arm by randomization. MSCs will be manufactured in our GMP facility and available to treat at least 36 patients. The study primary efficacy endpoint is improvement in clinical status at least two categories on a six-category ordinal scale at day 14 post randomization. The six-category ordinal scale ranges from 6 to 1 with a higher score indicates worse clinical outcome, i.e. 6 = death; 5 = hospitalization, requiring ECMO and/or IMV; 4 = hospitalization, requiring NIV and/or HFNC therapy; 3 = hospitalization, requiring supplemental oxygen (but not NIV/HFNC); 2 = hospitalization, not requiring supplemental oxygen; 1 = hospital discharge. The scale will be used to evaluate patients' status daily from baseline to day hospital discharge. Patients' clinical status at day 14 post randomization will be dichotomized as 'improved' (decreased by at least two categories) or 'not improved'. Patients who died before day 14 will be deemed as 'not improved'. Public data about the novel COVID-19 are limited and the data varies between all studies. Based on reported data, the time to improvement in patients with supportive care were about 22-23 days [20, 82] we expect 10% patients in the control group and 35%

patients in the MSC group will achieve 'improved' status at day 14, a total sample size of 66 (36 in the MSC arm and 30 in the control arm) will provide 84% power to detect a difference in clinical improvement of 25% between control (10%) and MSC (35%) at a 7.5% one-sided significance level using a Chi-square test.

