### 8.3 Randomization and Stratification

After safety run in, patients will be randomized in a 1:1 ratio to receive either MSCs or supportive care. Randomization will be stratified by severity of ARDS (moderate and severe), and employ permuted blocks method.

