### 8.4 Safety monitoring and stopping rule

This study will enroll the first 6 patients to the MSC arm for safety run in. Based on experience, we expect the toxicity of MSC is low about 5-10%. The chance of observing tSAEs in more than two out of six patients is 1.6%. After the first six patients complete safety monitoring at day 28, we will halt the study if more than two patients have tSAEs. Otherwise, the study will continue to enroll additional patients

The study will continuously monitor the safety of MSCs infusions in patients who are randomized to the MSC arm so that the accrual can be halted early if there is an unexpectedly high rate of treatment-related serious adverse events (tSAE) at day 28, defined in Section 7.4.5. Patients who don't complete the 28-day observation due to a reason other than tSAE will be deemed not evaluable for tSAE. However, those patients in the randomization phase are evaluable for efficacy and will not be replaced. A tSAE rate of greater than or equal to 25% is considered excessive. The occurrence of tSAEs will be monitored using a stopping guideline based on a Pocock-type boundary method [83]. The following sequential stopping boundaries will be used:

Number of Patients	1-3	4-5	6-7	8-9	10-12	13-14	15-17	18-20	21-23	24-26	27-28	29-30
Number of tSAEs <	-	4	5	6	7	8	9	10	11	12	13	14

The accrual will be halted if the number of tSAEs is equal to or exceeds the boundary in the above table. Under this sequential stopping rule, the probability of early stopping is 5% if the true tSAE rate is 25%, and the probability of early stopping will be high at 81% if the true tSAE rate is 50%.

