### 8.5 Statistical Analysis

All patients who received any MSC infusions in the MSCs arm or supportive care in the control arm will be included in the safety analyses. All efficacy analysis will be based on the intent to treat (ITT) population, defined as eligible and randomized subjects.

Adverse event data and corresponding toxicity grades after treatment will be summarized descriptively by treatment arms. All adverse events, grades, and attributions

will be listed and tabulated. Toxicity information including the type, severity, time of onset, time of resolution, and the probable association with the study regimen will be tabulated and summarized by treatment arms. Rate of tSAEs in patients treated with MSCs will be reported as proportion and its 95% confidence interval overall and by cancer status (cancer patients versus non-oncologic patients).

Clinical outcome data (increase in oxygen saturation, decrease in oxygen supplementation, progression to mechanical ventilation or ECMO, evolution of other end-organ damage, severity of ARDS, mortality rate, cause of death, duration on ventilation, durations of ICU stay and hospital stay, duration of vasopressor use, negative SARS-Co-V-2 RT-PCR by day 28, and change in disease severity scores and corticosteroid use) will be summarized descriptively. Categorical variables will be summarized by frequencies and percentages. Continuous variables will be summarized by means, standard deviations, medians, interquartile ranges.

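### The 84% power in section 8.2 counts six non-randomised run-in patients; the planned efficacy analysis is 30 v 30, with about 82% power

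*Combined protocol and SAP*

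**What the plan says.** Section 8.1 sets the order of events: "The study will first enroll and treat 6 patients with MSCs for safety run in, then additional 60 patients will be randomized". Section 8.4 confirms that the six are assigned rather than randomised: "This study will enroll the first 6 patients to the MSC arm for safety run in". Section 8.3 starts allocation only afterwards: "After safety run in, patients will be randomized in a 1:1 ratio to receive either MSCs or supportive care".

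Section 8.2 makes up the total of 66 from "6 patients for safety run in and additional 30 patients in each treatment arm by randomization". It then computes power on different arm sizes: "a total sample size of 66 (36 in the MSC arm and 30 in the control arm) will provide 84% power", for improvement rates of 10% (control) and 35% (MSC), "at a 7.5% one-sided significance level using a Chi-square test".

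Section 8.5 fixes the analysis set: "All efficacy analysis will be based on the intent to treat (ITT) population, defined as eligible and randomized subjects". Sections 2.3.1, 8.1 and 8.2 all time the primary efficacy endpoint at day 14 after randomisation.

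**The concern.** The sample-size statement and the analysis-population statement do not describe the same comparison. Since 36 = 30 + 6, the power calculation treats the run-in patients as part of the MSC arm, whereas section 8.5 leaves them out. The endpoint does not fit them either, because they have no randomisation date.

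Two things are at stake. First, the plan prints a size and power that do not belong to its own primary analysis. Second, naming 36 as the MSC arm invites someone to pool the run-in patients later. Under section 8.4 the six complete day-28 monitoring before accrual continues, so all of them precede every control. They are outside the stratification by ARDS severity, they are enrolled in the knowledge that they will receive MSC, and they all fall in one arm. A comparison that includes them is no longer fully randomised.

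**Working it through.** **Inputs.** Control rate p_C = 0.10, MSC rate p_T = 0.35, one-sided alpha 0.075 and a chi-square test, all from section 8.2. No continuity correction is mentioned, so none is used. The critical value is z = 1.4395. Arm sizes are n_T = 36, n_C = 30 (section 8.2) or n_T = n_C = 30 (sections 8.3 and 8.5).

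**Formula** (normal approximation, pooled variance under the null):

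- p̄ = (n_C·p_C + n_T·p_T)/(n_C + n_T)
- SE0 = √[p̄(1 − p̄)(1/n_C + 1/n_T)]
- SE1 = √[p_C(1 − p_C)/n_C + p_T(1 − p_T)/n_T]
- power = Φ[(0.25 − z·SE0)/SE1]

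**Step 1: reproduce the printed figure, 36 v 30.** p̄ = (3 + 12.6)/66 = 0.2364; SE0 = 0.1050; SE1 = 0.0965. Then (0.25 − 1.4395 × 0.1050)/0.0965 = 1.024 and Φ(1.024) = 84.7%. Exact enumeration of the uncorrected chi-square test gives 85.2%. The printed 84% is reproduced to within about a point, so 36 v 30 is what was used.

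**Step 2: the planned analysis, 30 v 30.** p̄ = (3 + 10.5)/60 = 0.2250; SE0 = 0.1078; SE1 = 0.1029. Then (0.25 − 1.4395 × 0.1078)/0.1029 = 0.921 and Φ(0.921) = 82.2%. Exact enumeration gives 83.6%.

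| Comparison | Patients | Pooled normal | Exact |
|---|---|---|---|
| 36 v 30 (section 8.2) | 66 | 84.7% | 85.2% |
| 30 v 30 (section 8.5) | 60 | 82.2% | 83.6% |

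On the pooled formula the fall is 84.7 − 82.2 = 2.5 points. Against the printed 84% it is 84 − 82.2 = 1.8 points (pooled) or 84 − 83.6 = 0.4 points (exact).

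**Step 3: what pooling would do to the error rate.** Suppose MSC has no effect and every randomised patient improves with probability 10%. The run-in improvement rate is varied; these rates are assumptions for illustration, not figures from the documents. The MSC count is then the sum of a binomial(30, 0.10) and a binomial(6, r), and the rejection probability of the one-sided 7.5% test is enumerated exactly.

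| Analysis | Assumed run-in rate r | One-sided error |
|---|---|---|
| 30 v 30 | not used | 6.9% |
| 36 v 30 | 10% (no bias) | 8.7% |
| 36 v 30 | 20% | 12.4% |
| 36 v 30 | 30% | 16.7% |

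The fair baseline for the pooled test is 8.7%, because with these small arms its exact size already exceeds the nominal 7.5%. The part due to run-in bias is 12.4 − 8.7 = 3.7 points or 16.7 − 8.7 = 8.0 points.

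**The case against.** The best reply is that the plan already answers the question. Section 8.5 is explicit, the endpoint is timed from randomisation, and section 8.4 speaks of patients in the randomisation phase as evaluable for efficacy. No section adds the run-in patients to the efficacy analysis. An explicit population definition should prevail over a sample-size sentence, and by the exact calculation 30 v 30 still rounds to 84%. All of this stands. It limits the size of the point but does not make section 8.2 right: the 66 and the 36 are still given as the basis of power for a comparison that will use 60 and 30.

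Three stronger readings are tempting, and the documents do not support them.

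- A reader might infer that the trial is underpowered. A change of about two points does not show that.
- A reader might infer that the plan leaves the primary population open, to be chosen once results are known. Only the power sentence points to 36; pooling would mean departing from section 8.5. The error rates of 12.4% and 16.7% therefore belong to an analysis that the plan excludes, and to assumed run-in rates.
- A reader might take the word eligible in the ITT definition as a plan to drop randomised patients with allocation known. Section 5.2 has eligibility verified before randomisation, and no section sets out later exclusions. The word is loose and worth tidying, no more.

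Whether 10% is a sound control rate is a separate matter: it bears on 36 v 30 and 30 v 30 alike.

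**Conclusion.** The point holds as an inconsistency of small size. The arithmetic behind 84% is correct for its inputs, but the inputs include six patients whom the planned analysis leaves out. The efficacy sample is 60, not 66, and its power is about 82% (82.2% pooled normal, 83.6% exact). This rests on section 8.2's own rates and significance level, on an uncorrected chi-square test, and on all 30 patients per arm being analysed. The practical value of correcting it is less in the two points than in removing the only text that could be cited for adding non-randomised patients to one arm.

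**What to change.** In section 8.2, state that the primary efficacy comparison includes the 60 randomised patients, 30 per arm, and that power is about 82% for 10% v 35% at one-sided 7.5%. Add that the six run-in patients contribute to safety and to a descriptive efficacy listing only, and label any pooled 36 v 30 analysis as supportive. Keep 66 as the total accrual, not as the basis of power.

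As a secondary clarification in section 8.5, define ITT as all randomised patients, analysed as randomised.

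The cost is wording, and a stated power about two points lower. No further patients are needed. If the sponsor prefers to keep 84%, the pooled formula requires 32 per arm: 64 randomised and 70 in total with the run-in. That would mean 32 + 6 = 38 patients treated with MSC, against the supply for at least 36 that section 8.2 describes.

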### 8.3 Randomization and Stratification

After safety run in, patients will be randomized in a 1:1 ratio to receive either MSCs or supportive care. Randomization will be stratified by severity of ARDS (moderate and severe), and employ permuted blocks method.

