### **2.3.1 Primary endpoints:**

1. Treatment-related serious adverse events (tSAEs)
2. Improvement by at least two categories on a six category ordinal scale at day 14 post randomization. The six-category ordinal scale is as follows:  
6 = death; 5 = hospitalization, requiring extracorporeal membrane oxygenation (ECMO) and/or invasive mechanical ventilation (IMV); 4 = hospitalization, requiring non-invasive mechanical ventilation (NIV) and/or High-flow nasal cannula (HFNC) therapy; 3 = hospitalization, requiring supplemental oxygen (but not NIV/HFNC); 2 = hospitalization, not requiring supplemental oxygen; 1 = hospital discharge.

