## **3 Eligibility Criteria**

### **3.1 Inclusion Criteria**

- 1) 18 years or older

- 2) Confirmed SARS-CoV2 infection real-time reverse transcription polymerase chain reaction (RT-PCR) assay
- 3) Moderate OR severe ARDS, based on the degree of impairment of oxygenation as defined by the ratio of arterial oxygen tension to fraction of inspired oxygen ( $\text{PaO}_2/\text{FiO}_2$ ):
  - a. Moderate ARDS:  $\text{PaO}_2/\text{FiO}_2$  100-200 mmHg
  - OR**
  - b. Severe ARDS:  $\text{PaO}_2/\text{FiO}_2 \leq 100$  mmHg
- 4) If on invasive or noninvasive (BiPAP) mechanical ventilator,  $\text{PEEP} \geq 5$  cm  $\text{H}_2\text{O}$
- 5) Bilateral opacities present on chest radiograph or computed tomographic (CT) scan, that are not fully explained by pleural effusions, lung collapse, or lung nodules.

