### 7.1 Baseline Pre-treatment Evaluation

- 7.1.1 History and physical (including vitals and oxygenation requirements)
- 7.1.2 SARS-CoV-2 RT-PCR testing
- 7.1.3 ARDS assessment
- 7.1.4 Complete Blood Count and differential (CBC)
- 7.1.5 Complete Metabolic Panel (CMP)
- 7.1.6 Coagulation studies: PT/aPTT, d-dimer, fibrinogen
- 7.1.7 Lactate Dehydrogenase (LDH)
- 7.1.8 C-Reactive Protein (CRP)
- 7.1.9 CXR and/or CT chest imaging
- 7.1.10 Urine or serum pregnancy test for females of childbearing potential
- 7.1.11 APACHE II score
- 7.1.12 Medical record review for concomitant medications
- 7.1.13 Clinical status assessed by the six-category ordinal scale (1 = discharged; 6 = death)

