Proportion of patients who have an improvement of at least two categories on a six category ordinal scale at day 14 and day 28 will be summarized using rate and their 95% confidence interval by treatment arms and compared with Chi-square tests. Proportion of patients with improvement will also be reported by cancer status. As exploratory analyses, improvement in clinical status will also be assessed using logistic regression, adjusting for potential confounders such as age, race/ethnicity, underlying condition, and severity of ARDS. Changes in the six-point ordinal scale, oxygen saturation, required FiO2, severity scores from baseline will be presented graphically and compared with paired t-tests or Wilcoxon signed rank tests, whichever are appropriate (comparisons are considered exploratory). Duration of overall survival will be days from date of randomization to date of death or date of last follow-up for censoring. Overall survival will be calculated using Kaplan-Meier survival curves with estimates of medians and 95% confidence intervals by each treatment arm and compared with a log-rank test (comparison is considered exploratory).

Laboratory data, which include inflammatory markers and chest imaging will be reported with appropriate summary statistics. Changes from baseline to post-treatment will be plotted for each patient over time and assessed using paired test methodologies when appropriate. Comparison between the two treatment groups will be exploratory with appropriate two-sample tests.

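### Starting category determines what a two-category improvement means, but no prespecified analysis of the primary endpoint names it

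*Combined protocol and SAP*

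**What the plan says.** **Entry.** Section 3.1 admits patients with moderate or severe ARDS, defined by PaO2/FiO2. The PEEP requirement is conditional: "If on invasive or noninvasive (BiPAP) mechanical ventilator". Section 3.2 excludes patients on ECMO but not those on invasive ventilation.

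**Endpoint.** Section 2.3.1 defines the primary efficacy endpoint as "Improvement by at least two categories on a six category ordinal scale at day 14 post randomization". Section 8.2 gives the scale, including "5 = hospitalization, requiring ECMO and/or IMV" and "4 = hospitalization, requiring NIV and/or HFNC therapy". Category 3 is supplemental oxygen without non-invasive ventilation (NIV) or high-flow nasal cannula (HFNC), 2 is in hospital without oxygen, and 1 is discharge.

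**Randomization.** Section 8.3 reads "Randomization will be stratified by severity of ARDS (moderate and severe), and employ permuted blocks method". Section 5.2 says the same. No other factor is listed.

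**Analysis.** Section 8.5 compares the day-14 proportions with a chi-square test and mentions no adjustment. An exploratory logistic regression follows, "adjusting for potential confounders such as age, race/ethnicity, underlying condition, and severity of ARDS".

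**Data.** Baseline category on the ordinal scale is collected (item 7.1.13 and the study calendar in 6.1).

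**The concern.** The endpoint is a change score on a coarse scale, so the starting point fixes the target:

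- from 5, the patient must be off invasive ventilation and off NIV/HFNC;
- from 4, off all supplemental oxygen;
- from 3, discharged.

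The chance of success may differ widely across these three targets. PaO2/FiO2 class is a different variable from the level of respiratory support, so stratifying on it need not balance the arms on starting category.

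With 30 patients per arm, a chance imbalance in the share intubated at entry would shift the observed day-14 difference. The primary test ignores starting category, and PaO2/FiO2 class is the only respiratory-severity measure that the exploratory model names. A reader of the final report could not easily tell how much of the result reflects treatment and how much reflects support at entry.

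**Working it through.** **1. The plan's own figure.** Inputs from 8.2: 10% v 35%, 36 MSC and 30 control, one-sided 7.5% (z = 1.4395). Pooled rate = (3 + 12.6)/66 = 0.2364. Standard error under no difference = 0.1050; under the alternative = 0.0965. Power = Φ[(0.25 − 1.4395 × 0.1050)/0.0965] = Φ(1.02) = 84.7%, which agrees with the stated 84%. The steps below use 30 v 30, because 8.5 limits efficacy analyses to randomized patients.

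**2. Error rate over all randomizations.** Assume 30 of 60 patients are intubated, with improvement rates under no effect of 2% (intubated) and 18% (not intubated), which is 10% overall as in 8.2. Averaging the exact rejection rate of the planned test over every possible split gives 6.9%. It is also 6.9% when both groups have a 10% rate. Both are below 7.5%.

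**3. How often the arms differ.** The number intubated in one arm of 30 is hypergeometric. If K of 60 are intubated and k of them fall in one arm, the arms differ by |2k − K|/30.

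| Intubated at entry (assumed) | Difference of 20 points or more, either direction |
|---|---|
| 12 of 60 | 10.4% |
| 20 of 60 | 17.0% |
| 30 of 60 | 19.6% |

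With 30 of 60, a difference that large in one given direction has probability 9.8%.

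**4. What the existing strata remove.** Assume 30 moderate and 30 severe patients, each split 15:15. With intubated shares (moderate/severe) of 20%/60%, 30%/70% and 40%/60%, the chance of a difference of 20 points or more is 15%, 16% and 19%. At 10%/80% it falls to 2.5%, although a difference of 10 points or more still has probability 47%.

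**5. Effect of exactly 20 points.** Put 12 intubated patients in one arm and 18 in the other. At 2%/18% with no treatment effect, the expected rates are 0.40 × 2% + 0.60 × 18% = 11.6% and 0.60 × 2% + 0.40 × 18% = 8.4%, a spurious difference of 3.2 points. The same sum gives 2.0 points at 5%/15% and 0.8 points at 8%/12%. Exact rejection rates of the one-sided 7.5% test, conditional on the split:

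| Rates, intubated/not | Favours MSC | Balanced | Favours control |
|---|---|---|---|
| 2%/18% | 13.2% | 6.2% | 2.5% |
| 5%/15% | 10.6% | 6.6% | 3.9% |
| 8%/12% | 8.3% | 6.8% | 5.6% |

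If MSC adds 25 points in both groups, power at 2%/18% is 91%, 84% and 74% in the same order.

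**6. Does a stratified test help?** A Cochran-Mantel-Haenszel test stratified by category 5 v 3–4, simulated 400,000 times per cell at 2%/18%, rejects 7.8%, 8.0% and 9.4% of the time under no effect. Its power is 84%, 85% and 83%. The dependence on the split largely disappears. The large-sample version runs slightly above 7.5% because events are sparse.

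**The case against.** The strongest reply is that randomization leaves every unstratified variable to chance, and the test remains valid. That stands. A reader might infer from the 13.2% that the trial's false-positive rate is inflated or its estimate biased. Step 2 shows otherwise: the 13.2% is conditional on an imbalance that arises in that direction or worse in about 10% of trials.

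A second reply is that 8.5 already allows for this. It is tempting to say that the adjusted model uses PaO2/FiO2 severity alone, or that no planned analysis could correct the imbalance. The documents support neither. The model also lists age, race/ethnicity and underlying condition, and its list is illustrative, so baseline category is unnamed rather than ruled out. Section 8.5 also plans to examine change from baseline on the ordinal scale, but with paired tests that do not adjust the comparison between arms. What remains is that nothing is prespecified by name. In an open-label trial, an open list permits covariates to be chosen after the results are seen.

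Third, the size rests on assumed rates and an assumed mix, and correlation between PaO2/FiO2 class and intubation reduces it. That stands, and at 8%/12% the effect is small. Entry in category 3 is also inferred from the conditional PEEP criterion, not stated. Entry in 4 and 5 does not depend on that inference.

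Fourth, grouping 3 with 4 still mixes two targets. That is true, and it is why improvement should also be reported for the three categories separately.

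**Conclusion.** The point holds as one of precision and interpretation. Starting category fixes what success means and is already recorded, yet it is absent from the randomization strata, from the primary test and from the named covariates. The planned test keeps its error rate on average (about 6.9%).

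Conditional on a 20-point imbalance, the false-positive rate could be anywhere from 13.2% or 2.5% down to 8.3% or 5.6%, depending on how strongly starting category predicts improvement. An imbalance of 20 points or more would occur in about 10% to 20% of trials if one fifth to one half of patients are intubated. Both ranges rest on assumptions, since the documents give neither the baseline mix nor rates by category. The trial remains valid without the change, but the change is cheap and should be made before any outcome comparison.

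**What to change.** In section 8.5:

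1. Prespecify the day-14 comparison as a Cochran-Mantel-Haenszel test stratified by baseline ordinal category (5 v 3–4), and align the test named in 8.2.
2. Add baseline category as a named covariate in the logistic model. No listed covariate needs to be removed.
3. Report day-14 improvement by arm for baseline categories 3, 4 and 5 separately.

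The cost is slightly more analysis work and no new data. The large-sample approximation is rough with few events, so an exact version of the stratified test can be specified.

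Adding baseline category (5 v 3–4) to the randomization strata in 5.2 and 8.3 is optional. It would give four cells for 60 patients. With small blocks in a single-center open-label trial, that brings incomplete blocks and more predictable assignments, and the analysis change does not depend on it.
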